In recent years, evidence of the antineoplastic activity of SSAs has emerged. Although objective radiographic responses associated with these agents are rare, many cases of prolonged disease stability have been documented in the literature, leading to the hypothesis that SSAs exert an inhibitory effect on tumor growth. Last year, results of a phase III randomized, placebo-controlled study, the PROMID trial, were published. In this trial, 85 patients with well-differentiated carcinoid tumors originating in the distal intestine and proximal colon (midgut) were randomized to receive either octreotide LAR 30 mg or placebo. Median progression-free survival was 14.3 months in the octreotide LAR group versus 6.0 months in the placebo group (p=0.000072), confirming the antiproliferative effect of octreotide in this patient population.⁵

Pasireotide (SOM230) is a novel somatostatin analog with a similar binding affinity to somatostatin sst₂ and substantially stronger binding affinities to ssts₁, ₃ and ₅ (see section 1.3).¹³ Preclinical data suggests that ssts₁, ₃ and ₅ play an important role in cell cycle arrest and induction of apoptosis.¹⁴ Thus, we hypothesize that pasireotide LAR may prove to be a more potent inhibitor of neuroendocrine tumor proliferation than octreotide LAR.

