11.2 Sample size justification

We plan to conduct a single-arm phase II trial, with the 12-month progression-free survival rate as the primary endpoint, and using a one-sided alpha level of 10%.

The null hypothesis is that PFS rate at 12 months will be 19%. With n=30 (plus up to 3 additional patients (10%) to account for early dropouts), we will have 90% power to reject the null, if the true 1-year PFS rate from this treatment regimen is 40% (these PFS rates correspond to null and alternative hypothesis median PFS of 5 and 9 months, respectively). The sample size calculations were conducted using nQuery Advisor 6.01.

The sample size was derived for the estimation of PFS at 1-year using binomial theory. If the survival distribution is exponential, a much tighter confidence interval for the 1-year survival is possible. We will first test for the exponentiality of the survival distribution using the Hollander=Proschan¹⁷ test. If the p-value for this preliminary test is greater than 0.20, we will provide the 90% lower confidence bound assuming an exponential distribution.

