11.3 Subset analyses

Neuroendocrine tumors are characterized by a heterogeneous rate of growth. Tumors originating in the distal small intestine and proximal colon (midgut carcinoid tumors) are characterized by a slower rate of metastatic growth than neuroendocrine tumors of other sites, including the lungs, stomach, pancreas and rectum. Therefore, a post-study subset analysis will evaluate PFS data based on site of primary tumor, distinguishing between two subsets:

Subset 1: Patients with neuroendocrine tumors of the distal small intestine and cecum (midgut carcinoids). Patients with mesenteric masses whose primary tumors are unidentified will be considered to have midgut carcinoid tumors.

Subset 2: Patients with advanced (metastatic or unresectable) neuroendocrine tumors of other primary sites (lung, stomach, duodenum, distal colon, rectum, pancreas) or unknown primary site.

Other subset analyses will distinguish patients with low-grade (grade 1) tumors versus intermediate grade (grade 2) tumors, and patients with low hepatic tumor burden (<10%) versus high hepatic tumor burden (>10%).

12 Exploratory Analysis

If available, archival tissue containing a tumor block (preferred) or 10 unstained slides (3-5 micron thick) representing biopsies from patient's primary or metastatic neuroendocrine tumor should be sent to Moffitt Cancer Center for correlative immunohistochemical studies. Specimens should be placed in a secure, airtight container, labeled with the patient name and study number.

Site should contact Moffitt Cancer Center at [contact] with expected delivery date.

Shipping address:

Attention [name]
Anatomic Pathology Dept.
H. Lee Moffitt Cancer Center
[name]
[name]

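### Section 11.2 lets a weak goodness-of-fit pre-test bring in an exponential 90% bound for 12-month PFS, without saying which result decides; the bound can be too optimistic when sites differ strongly and follow-up is long

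*Combined protocol and SAP*

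**What the plan says.** Section 11.2 names the 12-month PFS rate as primary endpoint and tests 19% against 40% at one-sided 10%. It claims 90% power with 30 patients and says the size comes from binomial theory. It then argues that an exponential model would give a much tighter interval and sets a two-step rule: "We will first test for the exponentiality of the survival distribution using the" Hollander-Proschan test, followed by "If the p-value for this preliminary test is greater than 0.20, we will provide the 90% lower confidence bound assuming an exponential distribution".

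Section 11 leaves four things open:
- whether the exponential bound or the binomial test decides rejection of 19%;
- what is reported when p is 0.20 or less;
- whether the exponential rate in the pre-test is estimated from the data;
- when the data are cut.

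Section 11.3 opens with "Neuroendocrine tumors are characterized by a heterogeneous rate of growth" and says midgut tumours grow more slowly than those of other sites. Both groups are pooled in the primary analysis.

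**The concern.** The form of the bound depends on a non-significant result from the same 30 or so patients. Failing to reject exponentiality in a sample that small is weak evidence for it.

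The plan also gives a reason to doubt the assumption. If each site had exponential PFS at its own rate, the pooled curve would be a mixture with a falling hazard, which is not exponential. An exponential fit uses all follow-up time, so a few slow growers followed for years raise the fitted 12-month value even when the true 12-month rate is 19%.

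Two things are at stake. The decision rule is incomplete, which leaves room to choose between two results after the data are seen. And a bound presented as 90% can have more than 10% one-sided error.

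**Working it through.** **1. The plan's own figure.** Exact binomial, n = 30, reject if at least 9 are progression-free at 12 months: P(X ≥ 9 | 0.19) = 0.1004 and P(X ≥ 9 | 0.40) = 0.906. At the unrounded medians, 2^(-12/5) = 0.1895 and 2^(-12/9) = 0.3969, these are 0.0990 and 0.900. The stated design is reproduced by the binomial rule alone, whatever the shape of the curve.

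**2. Why the pre-test nearly always passes when the curve is exponential.** The statistic is the sum of S0(t) times the Kaplan-Meier jump. Without censoring its scaled variance is 1/12 if S0 is fully specified, but 1/12 − 1/16 = 1/48 if the rate is estimated. The SD is then √(12/48) = 0.5 of its nominal value. The condition p > 0.20 means |Z| < 1.282, so the pass probability is P(|N(0,1)| < 1.282/0.5 = 2.563) ≈ 0.99, not the nominal 0.80. Simulation at n = 30 with staggered censoring gives over 99%.

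**3. Power against a site mix.** The midgut share is not given; 10-70% was assumed. With at least 12 months' follow-up the pre-test still passes in 97-100% of trials at a hazard ratio of 2 between sites and in 90-99.9% at 3.

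**4. Mixes used.** The only PFS anchors are for midgut tumours in the cited placebo-controlled trial (Section 1.2): "Median progression-free survival was 14.3 months in the octreotide LAR group versus 6.0 months in the placebo group". The median for the other sites is solved so that total 12-month PFS is exactly 19%:
- Midgut 14.3 months: S(12) = 2^(-12/14.3) = 0.559. At a 20% share the rest have (0.19 − 0.2 × 0.559)/0.8 = 0.098, median 3.6 months. At 30%, (0.19 − 0.3 × 0.559)/0.7 = 0.032, median 2.4 months.
- Midgut 6.0 months: S(12) = 0.25. At 30% and 50% shares the rest have 0.164 and 0.130, medians 4.6 and 4.1 months.

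**5. Two-step error at a true 19% (nominal 0.10).** The simulation used n = 30, an estimated rate, a two-sided p, exact progression times and a chi-square exponential bound. The assumed fallback when p ≤ 0.20 is at least 9/30.

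| Follow-up (assumed) | True curve | Pre-test passes | Two-step error |
|---|---|---|---|
| 12 months or more | exponential | over 99% | about 0.10 |
| 12-36 months | midgut 6.0 in 30-50% | over 99% | 0.10-0.11 |
| 12-24 months | midgut 14.3 in 20-30% | 88-99% | 0.11-0.12 |
| 12-36 months | intermediate mixes | not tabulated | 0.12-0.13 |
| 12-36 months | midgut 14.3 in 20-30% | 82-97% | 0.15-0.16 |
| at least 36 months | midgut 14.3 in 20-30% | 54-86% | 0.19-0.23 |

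The plan gives no formula for the bound under censoring. A slightly more conservative version lowers the errors by 0.01-0.02; at 12-24 months, for example, the error given a pass is then 0.085-0.104. With all data cut at 12 months the error is below 0.10. Results at n = 35 are similar.

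**6. What the exponential model gains.** Without censoring, the binomial SE is √(S(1−S)/30) and the exponential SE is S|ln S|/√30. At 19%: √(0.19 × 0.81/30) = 0.072 against 0.19 × 1.661/5.477 = 0.058. At 40%: √(0.40 × 0.60/30) = 0.089 against 0.40 × 0.916/5.477 = 0.067. The SE falls by 20-25%.

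**The case against.** Four objections carry weight.

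First, a reader might infer that the pre-test almost never fails. That holds for exponential data and mild mixes only. In the strongest mixes with at least 36 months' follow-up it fails in 14-46% of trials, so it gives partial protection where the bound is worst.

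Second, a reader might infer that the error does exceed 10%. The documents do not establish this. The excess needs follow-up well past 12 months and a large difference between sites. The 14.3 months was observed on octreotide LAR, and the other-site medians are back-solved. The 2.4-month value is shorter than one 84-day scan interval, and Section 11.3 says only that midgut tumours grow more slowly. With a midgut median of 6.0 months there is almost no excess. Long follow-up is nevertheless foreseeable: Section 7.2 schedules scans beyond five years and Section 8 runs PFS to an unspecified cut-off.

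Third, a reader might infer that the exponential bound replaces the binomial test. The text says only that the bound will be provided, and the sizing is binomial. What stands is that the deciding result is not named.

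Fourth, a reader might take the pre-test rate as fixed at the null median of 5 months, which would turn the pre-test into a test of the drug effect. The text speaks of testing exponentiality, so an estimated rate is the natural reading.

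**Conclusion.** The concern holds as a gap in the analysis rule and a conditional risk; the plan should be changed. Two parts need no simulation: Section 11.2 does not name the result that decides rejection of 19%, and it defines nothing for p ≤ 0.20. A third follows from the test itself: with an estimated rate and 30 patients it cannot vouch for the exponential bound against mild to moderate site mixes, which Section 11.3 gives reason to expect.

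If the exponential bound is used to judge 19%, the two-step error is about 0.10-0.12 with 12-24 months' follow-up or a small difference between sites. It is 0.13-0.16 with 12-36 months and a strong mix, and 0.19-0.23 with at least 36 months and a strong mix. These figures rest on assumed midgut shares, medians, cut-offs and fallback, none of which the documents give. They show what could happen and do not estimate this trial's error rate.

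**What to change.** Remove the pre-test as a selector and make the binomial test that the trial was sized on the only primary analysis. State the rejection rule as a count, with its own error and power:

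| Patients analysed | Reject 19% if progression-free at 12 months | Alpha | Power at 40% |
|---|---|---|---|
| 30 | at least 9 | 0.1004 | 0.906 |
| 30 | at least 10 | 0.045 | 0.824 |
| 35 | at least 10 | 0.113 | 0.943 |
| 35 | at least 11 | 0.055 | 0.888 |

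Do not write the rule as a Clopper-Pearson 90% lower bound above 19%. At 9/30 that bound is 0.1899, so the rule would need 10/30 and power would fall to 0.824. Section 11.1 enrols 35 while Section 11.2 uses 30. Settle the number analysed and take the cut-off from it; at 35 no cut-off has both alpha of at most 0.10 and 90% power.

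State the data cut-off and how patients censored before 12 months are counted. A Kaplan-Meier 12-month estimate may be used for early censoring if its decision rule is fixed in advance. Keep the exponential bound as a labelled supportive analysis.

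The cost is a few sentences in Section 11.2 and a larger standard error than the exponential model gives (0.072 against 0.058 at 19%; 0.089 against 0.067 at 40%, without censoring). The planned power at n = 30 is kept, because it never relied on the exponential model.

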11.3 Subset analyses

Neuroendocrine tumors are characterized by a heterogeneous rate of growth. Tumors originating in the distal small intestine and proximal colon (midgut carcinoid tumors) are characterized by a slower rate of metastatic growth than neuroendocrine tumors of other sites, including the lungs, stomach, pancreas and rectum. Therefore, a post-study subset analysis will evaluate PFS data based on site of primary tumor, distinguishing between two subsets:

Subset 1: Patients with neuroendocrine tumors of the distal small intestine and cecum (midgut carcinoids). Patients with mesenteric masses whose primary tumors are unidentified will be considered to have midgut carcinoid tumors.

Subset 2: Patients with advanced (metastatic or unresectable) neuroendocrine tumors of other primary sites (lung, stomach, duodenum, distal colon, rectum, pancreas) or unknown primary site.

Other subset analyses will distinguish patients with low-grade (grade 1) tumors versus intermediate grade (grade 2) tumors, and patients with low hepatic tumor burden (<10%) versus high hepatic tumor burden (>10%).

12 Exploratory Analysis

If available, archival tissue containing a tumor block (preferred) or 10 unstained slides (3-5 micron thick) representing biopsies from patient's primary or metastatic neuroendocrine tumor should be sent to Moffitt Cancer Center for correlative immunohistochemical studies. Specimens should be placed in a secure, airtight container, labeled with the patient name and study number.

Site should contact Moffitt Cancer Center at [contact] with expected delivery date.

Shipping address:

Attention [name]
Anatomic Pathology Dept.
H. Lee Moffitt Cancer Center
[name]
[name]

Immunohistochemistry (IHC) will be used to evaluate the expression of somatostatin receptors (SSTs₁₋₅). Sections of 3-4 microns in thickness will be cut from the selected formalin-fixed paraffin embedded tissue and subjected to IHC staining protocol using the Dakocytomation Autostainer (DakoCytomation, Carpinteria, Calif). Microwave antigen retrieval with IHC Select EDTA buffer, pH 7.5, will be utilized. Rabbit polyclonal primary antibodies against SST₁₋₅ with cross-reactivity against human SST subtypes will be diluted and incubated for 60 minutes at room temperature. Using a semiquantitative scoring system, the intensity of IHC staining for various SST subtypes will be scored as either 0 (negative), 1+ (mild positive staining), 2+ (moderate positive) and 3+ (strong positive staining). The correlation between SST staining patterns and clinical outcomes (PFS) will be analyzed in a descriptive fashion.

We will also explore the correlation between early biochemical response and PFS. Early biochemical responders will be defined as patients with elevated chromogranin A (CgA) who experience a major reduction (>50%) or normalization of their CgA between their baseline (pretreatment) measurement and their follow-up assessment 3 months later.

13 Quality of Life Assessment

Patient quality of life will be measured using the EORTC QLQ-C30 (version 3) and the EORTC QLQ GI.NET21 questionnaires (appendices B and C). The EORTC QLQ-C30 questionnaire is designed to assess the health-related quality of life of cancer patients participating in clinical trials. It is composed of 5 functional scales, three symptom scales, a global health status scale, and six single items. The EORTC QLQ GI.NET21 questionnaire is

designed to assess physical and psychological symptoms related to neuroendocrine tumors of the gastrointestinal tract.

Both questionnaires will be scored and handled as recommended in the user manual. Missing items will be imputed with the mean of the non-missing items scored at that assessment time point. Ambiguous items will be considered as missing items. At each assessment time point, summary statistics of the raw score and linear transformation score (on a 0-100 scale) will be provided.

14 Protocol amendments, or changes in study conduct

Any change or addition (excluding administrative) to this protocol requires a written protocol amendment that must be reviewed by Recordati Inc. and the investigator before implementation. Amendments significantly affecting the safety of subjects, the scope of the investigation or the scientific quality of the study require additional approval by the IRB at each study center. A copy of the written approval of the IRB must be provided to Recordati Inc. Examples of amendments requiring such approval are:

1. increases in drug dose or duration of exposure of subjects,
2. significant changes in the study design (e.g. addition or deletion of a control group),
3. increases in the number of invasive procedures,
4. addition or deletions of a test procedure required for monitoring of safety.

These requirements for approval should in no way prevent any immediate action from being taken by the investigator or by Recordati Inc. in the interests of preserving the safety of all patients included in the trial. If an immediate change to the protocol is felt to be necessary by the investigator and is implemented for safety reasons Recordati Inc. must be notified and the IRB at the center must be informed immediately.

15 Procedures and Instructions

15.1.1 Publication of results

Any formal presentation or publication of data from this trial may be published after review and comment by Recordati Inc. and prior to any outside submission. Recordati Inc. must receive copies of any intended communication in advance of publication (at least fifteen working days for presentational materials and abstracts and thirty working days for manuscripts). These requirements acknowledge Recordati Inc.'s responsibility to provide peer input regarding the scientific content and conclusions of such publications or presentations. Principal Investigation/Institution shall have the final authority to determine the scope and content of its publications, provided such authority shall be exercised with reasonable regard for the interests of Recordati Inc. and, in accord with the trial contract and shall not permit disclosure of Recordati Inc. confidential or proprietary information.

15.1.3 Discontinuation of study

Recordati Inc. reserves the right to discontinue any study under the conditions specified in the clinical trial agreement.

15.2 Ethics and Good Clinical Practice

This study must be carried out in compliance with the protocol and the principles of Good Clinical Practice, as described in Recordati Inc. standard operating procedures and:

ICH Harmonized Tripartite Guidelines for Good Clinical Practice 1996. Directive 91/507/EEC, The Rules Governing Medicinal Products in the European Community.

US 21 Code of Federal Regulations dealing with clinical studies (including parts 50 and 56 concerning informed consent and IRB regulations).

Declaration of Helsinki and amendments, concerning medical research in humans (Recommendations Guiding Physicians in Biomedical Research Involving Human Subjects).

The investigator agrees to adhere to the instructions and procedures described in it and thereby to adhere to the principles of Good Clinical Practice that it conforms to.

15.2.1 Institutional Review Board/Independent Ethics Committee

Before implementing this study, the protocol, the proposed informed consent form and other information to subjects, must be reviewed by a properly constituted Institutional Review Board/Independent Ethics Committee/Research Ethics Board (IRB/IEC/REB). A signed and dated statement that the protocol and informed consent have been approved by the IRB/IEC/REB must be given to Recordati Inc. before study initiation. Any amendments to the protocol, other than administrative ones, must be reviewed by Recordati Inc. approved by this committee.

15.2.2 Informed consent

The investigator must explain to each subject (or legally authorized representative) the nature of the study, its purpose, the procedures involved, the expected duration, the potential risks and benefits involved and any discomfort it may entail. Each subject must be informed that participation in the study is voluntary and that he/she may withdraw from the study at any time and that withdrawal of consent will not affect his/her subsequent medical treatment or relationship with the treating physician.

This informed consent should be given by means of a standard written statement, written in non-technical language. The subject should read and consider the statement before signing and dating it, and should be given a copy of the signed document. If the subject cannot read or sign the documents, oral presentation may be made or signature given by the subject's legally appointed representative, if witnessed by a person not involved in the study, mentioning that the patient could not read or sign the documents. No patient can enter the study before his/her informed consent has been obtained.

The informed consent form is considered to be part of the protocol, and must be submitted by the investigator with it for IRB/IEC/REB approval.

Appendix A: List of Drugs Known to Promote QT Prolongation

This is not a comprehensive list of medications which may prolong the QT interval.

Albuterol*
Amiodarone
Arsenic trioxide
Bepridil
Chlorpromazine
Chloroquine
Cisapride
Clarithromycin
Disopyramide
Dofetilide
Domperidone
Droperidol
Erythromycin
Halofantrine
Haloperidol
Ibutilide
Levomethadyl
Mesoridazine
Methadone
Pentamidine
Pimozide
Procainamide
Quinidine
Salbutamol*
Sotalol
Sparfloxacin
Thioridazine

*Parenteral preparations only; inhaled treatments at usual doses are acceptable

EORTC QLQ-C30 (version 3)

We are interested in some things about you and your health. Please answer all of the questions yourself by circling the number that best applies to you. There are no "right" or "wrong" answers. The information that you provide will remain strictly confidential.

Please fill in your initials:

--	--	--	--	--

Your birthdate (Day, Month, Year):

--	--	--	--	--	--	--	--	--	--

Today's date (Day, Month, Year):

31

--	--	--	--	--	--	--	--	--	--

	Not at All	A Little	Quite a Bit	Very Much
1. Do you have any trouble doing strenuous activities, like carrying a heavy shopping bag or a suitcase?	1	2	3	4
2. Do you have any trouble taking a long walk?	1	2	3	4
3. Do you have any trouble taking a short walk outside of the house?	1	2	3	4
4. Do you need to stay in bed or a chair during the day?	1	2	3	4
5. Do you need help with eating, dressing, washing yourself or using the toilet?	1	2	3	4

During the past week:

	Not at All	A Little	Quite a Bit	Very Much
6. Were you limited in doing either your work or other daily activities?	1	2	3	4
7. Were you limited in pursuing your hobbies or other leisure time activities?	1	2	3	4
8. Were you short of breath?	1	2	3	4
9. Have you had pain?	1	2	3	4
10. Did you need to rest?	1	2	3	4
11. Have you had trouble sleeping?	1	2	3	4
12. Have you felt weak?	1	2	3	4
13. Have you lacked appetite?	1	2	3	4
14. Have you felt nauseated?	1	2	3	4
15. Have you vomited?	1	2	3	4
16. Have you been constipated?	1	2	3	4

Please go on to the next page

ENGLISH

During the past week:

	Not at All	A Little	Quite a Bit	Very Much
17. Have you had diarrhea?	1	2	3	4
18. Were you tired?	1	2	3	4
19. Did pain interfere with your daily activities?	1	2	3	4
20. Have you had difficulty in concentrating on things, like reading a newspaper or watching television?	1	2	3	4
21. Did you feel tense?	1	2	3	4
22. Did you worry?	1	2	3	4
23. Did you feel irritable?	1	2	3	4
24. Did you feel depressed?	1	2	3	4
25. Have you had difficulty remembering things?	1	2	3	4
26. Has your physical condition or medical treatment interfered with your family life?	1	2	3	4
27. Has your physical condition or medical treatment interfered with your social activities?	1	2	3	4
28. Has your physical condition or medical treatment caused you financial difficulties?	1	2	3	4

For the following questions please circle the number between 1 and 7 that best applies to you

29. How would you rate your overall health during the past week?

1 2 3 4 5 6 7

Very poor

Excellent

30. How would you rate your overall quality of life during the past week?

1 2 3 4 5 6 7

Very poor

Excellent

